^o Blood samples will be collected for PK analysis of VX-561 and metabolites or IVA and metabolites. The sample collected at Screening will be collected without regard to time of IVA dosing. On Day 1, samples will be collected before dosing (0 hours) and at 4 hours after dosing (relative to the morning dose). At Day 15, Week 4, Week 8, and Week 12, a predose sample will be collected before the morning dose. In a subset of subjects (up to approximately 20 subjects), additional samples will be collected at the Week 4 visit at 1, 2, 4, and 6 hours after dosing (relative to the morning dose). At the Washout Visit, a single sample will be collected prior to resumption of IVA. A single sample will be collected at the Safety Follow-up Visit for analysis of IVA for those subjects who resume IVA therapy. Acceptable PK sampling windows are provided in Table 11-1. At the ETT Visit, a single blood sample for PK analysis will be collected.

^p Study drug will be administered orally twice daily (Section 9.6). The last dose of study drug will be the morning dose on the Week 12 Visit. Subjects may resume their prior IVA therapy after the Washout Visit.

^q All medications taken from 28 days before the Screening Period through the end of the study will be recorded (Section 9.5).

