9.6 Administration

Study drug will be administered orally twice daily. Subjects will receive the same number of tablets each day to maintain the blind. Additional information is provided in the Pharmacy Manual.

Study drug will be administered with a fat-containing meal or snack, consistent with the recommendations for administration of Kalydeco¹², according to the following guidelines:

- It is recommended that the dose be taken within 30 minutes of the start of the meal or snack.
- All study drug doses will be administered q12h to maintain the blind. All doses of study drug will be taken at approximately the same time each day. For example, the morning dose could

be taken at 08:00 every morning and the evening dose could be taken at 20:00 every evening throughout the study.

- The date, amount taken, and time of study drug administration, including whether food was taken with each dose, will be recorded for the 2 doses before PK sample collection and the dose received on the morning of PK sample collection.
- On days of scheduled visits, the morning dose of study drug will be administered at the site after predose assessments have been completed. The meal or snack will be provided by the site for the morning dose of study drug.
- A subject's morning dose can be delayed by up to 6 hours to accommodate predose assessments on clinic visit days.
- For visits after the Day 1 Visit, subjects will be instructed to bring all used and unused study drug to the site; study drug will be dispensed at each visit, as appropriate.

Missed Doses

- If a subject misses a dose and recalls the missed dose within 6 hours, the subject should take the dose with food. If more than 6 hours have elapsed after the usual dosing time, the subject should skip that dose and resume the normal schedule for the following dose.

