11.3 Pharmacodynamics: Sweat Chloride

Collection of sweat samples will be performed using an approved collection device.

Each collection will occur before study drug dosing. At each time point, 2 samples will be collected, 1 from each arm (left and right). Additionally, sweat collections will be performed on any single day during screening.

Sweat samples will be sent to a central laboratory for testing and interpretation of results. Sweat chloride results for individual subjects will not be disclosed to the study sites.

Specific instructions for collection, handling, processing, and shipping of sweat chloride samples to the central laboratory will be provided in a separate Laboratory Manual.

See Section 10.7.1 for information about blinding of sweat chloride results.

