11.4 Efficacy: Spirometry

Spirometry will be performed according to the American Thoracic Society Guidelines/European Respiratory Society Guidelines.⁹

Spirometry will be performed as outlined below:

Pre-bronchodilator spirometry is defined as spirometry testing performed for subjects who have

- withheld their short-acting bronchodilators (e.g., albuterol and ipratropium bromide [Atrovent[®]]) for more than 4 hours before the spirometry assessment;
- withheld their twice daily, long-acting bronchodilator (e.g., salmeterol) for more than 12 hours before the spirometry assessment; and
- withheld their once-daily, long-acting bronchodilator (e.g., tiotropium bromide [Spiriva[®]]) for more than 24 hours before the spirometry assessment.

During the Screening Period, spirometry assessments may be performed pre- or post-bronchodilator. At all other visits, all spirometry assessments should be performed “pre-bronchodilator”. During the Treatment Period, spirometry assessments must be performed before the morning dose of study drug at approximately the same time at each visit.

In the event that a subject forgets to withhold bronchodilator(s), spirometry should be performed according to the following:

- If a subject’s Day 1 Visit spirometry assessment is pre-bronchodilator but, on a subsequent visit, the subject forgets to withhold bronchodilator use, a post-bronchodilator spirometry assessment will be obtained for that visit only, and the visit will not be rescheduled.
- If, on the Day 1 Visit, the subject forgets to withhold his/her dose of bronchodilator, spirometry should be performed post-bronchodilator, and all subsequent spirometric measurements (according to the schedule of assessments detailed in Table 3-1) should be performed post-bronchodilator.
- Each spirometry assessment will be recorded in the source documents as pre- or post-bronchodilator.

If more than 1 spirometry assessment is required at a visit, bronchodilators will be withheld until completion of the last scheduled spirometry assessment.

All sites will be provided with spirometers to be used for all study assessments. Spirometry data will be transmitted to a centralized spirometry service for quality review. The investigator's assessment of the spirometry results will be used for the screening assessment and determination of eligibility.

See Section 10.7.1 for information about blinding of spirometry results.

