11 LIST OF APPENDICES

Appendix A: Analysis Visit Windows for Safety and Efficacy Assessments

Table 11-1 Analysis Visit Windows for Safety and Efficacy Assessments			
Assessment	Visit¹	Target Study Day	Analysis Visit Window (in study days)^{2,3,4}
Safety Analysis			
Serum Chemistry Hematology Weight/BMI	Day 1 (Baseline)	1	≤1 Pre-dose
	Day 15	15	[1, 22] Day 1 post dose
	Week 4	29	(22, 43]
	Week 8	57	(43, 71]
	Week 12	85	(71, 99]
	Safety Follow-up	Not applicable	Use nominal visit
Coagulation	Day 1 (Baseline; before dosing)	1	Use nominal visit for all post-baseline visits
	Week 12	Not applicable	
	Safety Follow-up	Not applicable	
Vital Signs Pulse Oximetry	Day 1 (Baseline)	1	≤1 Pre-dose
	Day 15	15	[1, 22] Day 1 post dose
	Week 4	29	(22, 43]
	Week 8	57	(43, 71]
	Week 12	85	(71, Week 12 visit date ⁵)
	Washout Visit	Not applicable	Use nominal visit
	Safety Follow-up	Not applicable	Use nominal visit
Standard 12-Lead ECG	Day 1 (Baseline; before dosing)	1	Use nominal visit for all post-baseline visits
	Week 4	Not applicable	
	Safety Follow-up	Not applicable	
Efficacy and Pharmacodynamic Analysis			
Spirometry ⁶ Sweat Chloride ⁶	Day 1 (Baseline)	1	≤1 Pre-dose
	Day 15	15	(1, 22]
	Week 4	29	(22, 43]
	Week 8	57	(43, 71]
	Week 12	85	(71, Week 12 visit date ⁵)
	Washout Visit	Not applicable	Use nominal visit
	Safety Follow-up	Not applicable	Use nominal visit
Notes:			
1 Visit name for analysis purpose is used to report data in tables and figures.			
2 The analysis visit windows will be applied using the following rules for both scheduled and unscheduled visits:			
a. If no numerical measurement is available within a visit window, the measurement will be considered missing for the visit.			
b. If there is more than 1 numerical measurement available within the same visit window, use the following rules:			
i. The measurement closest to the target day will be used; or			
ii. If there are multiple measurements within the same distance from the target day, the latest measurement will be used.			
3 For measurements collected on the date of first dose of study drug, if it cannot be determined whether the measurements are before or after the first dose:			
a. Scheduled measurement will be treated as pre-dose observation.			
b. Unscheduled measurement will be treated as post-dose observation.			

Table 11-1 Analysis Visit Windows for Safety and Efficacy Assessments			
Assessment	Visit¹	Target Study Day	Analysis Visit Window (in study days)^{2,3,4}

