
4. When the ETT visit replaces the Safety Follow-up visit, it will be mapped to the Safety Follow-up visit. Other ETT visits will be mapped according to the analysis visit windowing rule for safety analysis.
 
5. If the week 12 visit is not available, then no assessment will be mapped to the Week 12 analysis visit.
 
6. Except for safety follow-up visit (or ETT replacing safety follow-up visit) and washout visit (given that Week 12 visit is completed), spirometry and sweat chloride assessments after last dose date will not be mapped to analysis visits.
 
Derived Variables
 
1. Age (in years) at first dose date and nominal visit (for demographics, listing and the calculation of [percent] predicted spirometry variable)
 
Obtain age at informed consent (in days) in “yy, mm” format (e.g., 24 years, 6 months) from Vital Signs page at the Screening Visit, and add 0.5 month to convert to days.
 
Obtain informed consent date.
 
Then age (in years) at first dose date or nominal visit = [(first dose date or nominal visit date – informed consent date) in days + age at informed consent (in days)]/365.25.
 
2. Missing first dose date or last dose date
 
If the first dose date is missing, use Day 1 visit date to impute.
 
If the last dose date is missing or partial date is reported, the last dose date will be imputed based on, in descending order priority, the Early Treatment Termination (ETT) visit date, last visit date before the Safety Follow-up, or the last study drug administration date from EX SDTM domain, as appropriate. The imputation algorithm will ensure the imputed last dose date does not exceed the study participation end date.
 
3. Sweat Chloride:
 
Non-missing sweat chloride concentrations from the left arm and right arm with the assessment end date/time for a given arm up to 30 minutes after first dose time in treatment period will be considered for baseline.
 
4. Electrocardiogram:
 
Baseline is defined as the most recent pretreatment measurement before the first dose of study drug in the Treatment Period (or the average of triplicate measurements, if the most recent non-missing measurement is obtained in triplicate at screening). If multiple ECG measurements are obtained on the same visit during the TE period,
 
 ○ For summary purpose, the nominal scheduled ECG will be used as the ECG value for the visit; ○ For threshold analysis purpose, all reported ECG values will be used. 			

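### SAP Appendix A, note 6, has no exception for the Week 12 visit, so a predose Week 12 ppFEV1 or sweat chloride value is dropped if that morning's dose is not taken (minor)

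*SAP*

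**What the plan says.** The mapping rule is in SAP Appendix A, Table 11-1. The rows for spirometry and sweat chloride carry note 6: "spirometry and sweat chloride assessments after last dose date will not be mapped to analysis visits". Its exceptions are the Safety Follow-up visit, an ETT visit that replaces it, and the "washout visit (given that Week 12 visit is completed)". The Week 12 visit is not among them. Note 2a adds: "If no numerical measurement is available within a visit window, the measurement will be considered missing for the visit". Note 5 only removes Week 12 mapping when there is no Week 12 visit.

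The protocol fixes the order of events on the day:

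- Section 11.4: "During the Treatment Period, spirometry assessments must be performed before the morning dose of study drug".
- Section 11.3, on sweat chloride: "Each collection will occur before study drug dosing".
- Section 3, Table 3-1, footnote p: "The last dose of study drug will be the morning dose on the Week 12 Visit".
- Section 9.6: "On days of scheduled visits, the morning dose of study drug will be administered at the site after predose assessments have been completed". All arms dose every 12 hours to keep the blind.

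SAP 8.1 does not impute missing data unless otherwise specified, and SAP 8.3.1.3 plans no sensitivity analysis of the primary variable.

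**The concern.** A rule that removes values dated after the last dose is normally meant to keep off-treatment measurements out of the analysis. Here it can also remove an on-treatment one. At Week 12 the measurement comes first and the last planned dose second. If that dose is not taken, the last dose date falls back to the previous calendar day, and the value just collected counts as post-treatment.

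Two subjects with identical dosing up to the measurement are then handled differently because of one tablet due after it. Week 12 is the only scheduled visit where omitting that morning's dose alone has this effect, because at earlier visits later doses follow. What is at stake is a Week 12 value of the primary endpoint, or of the secondary sweat chloride endpoint, collected as planned but not analysed.

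**Working it through.** **1. Apply note 6 literally.** Put the Week 12 visit on its target day, Day 85.

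| Week 12 morning dose | Last dose date | Week 12 assessment date | After last dose date? | Week 12 value |
|---|---|---|---|---|
| Taken | Day 85 | Day 85 | No | Mapped |
| Not taken; last dose evening of Day 84 | Day 84 | Day 85 | Yes | Not mapped |

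With the example clock in protocol 9.6 (08:00 and 20:00), an 08:00 measurement is 12 hours after the last tablet in both rows. In the second row Week 12 is missing under note 2a, unless an unscheduled measurement after Day 71 and no later than the last dose date fills the window.

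**2. Reproduce the planned precision.** Inputs from protocol 12.1 and SAP 6.2: SD 7 points, 10% dropout, 2-sided 95% CI, 1-sample t. Half-width = t(0.975, n−1) × 7/√n, with completers n rounded down.

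| Planned N | 0.9 × N | n | Half-width | Stated |
|---|---|---|---|---|
| 28 | 25.2 | 25 | 2.889 | 2.9 |
| 22 | 19.8 | 19 | 3.374 | 3.4 |
| 14 | 12.6 | 12 | 4.448 | 4.4 |
| 11 | 9.9 | 9 | 5.381 | 5.4 |

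All four stated figures are reproduced.

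**3. Cost of one lost Week 12 value in an arm.** The MMRM recovers part of the loss from earlier visits. Assume Week 8 is observed and its correlation with Week 12 is r. The documents give no correlation, so take r = 0.5 to 0.8. Then

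SE after the loss = 7 × √[(1 − r²)/(n − 1) + r²/n], against 7/√n before it.

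The ratio simplifies to √[1 + (1 − r²)/(n − 1)].

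| Arm | n | r = 0.5 | r = 0.8 |
|---|---|---|---|
| VX-561 | 25 | √(1 + 0.75/24) = 1.0155, +1.5% | √(1 + 0.36/24) = 1.0075, +0.7% |
| VX-561 | 19 | √(1 + 0.75/18) = 1.0206, +2.1% | √(1 + 0.36/18) = 1.0100, +1.0% |
| IVA | 12 | √(1 + 0.75/11) = 1.0335, +3.4% | √(1 + 0.36/11) = 1.0162, +1.6% |
| IVA | 9 | √(1 + 0.75/8) = 1.0458, +4.6% | √(1 + 0.36/8) = 1.0223, +2.2% |

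The ranges are 0.7–2.1% in a VX-561 arm and 1.6–4.6% in the IVA arm.

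**4. Degrees of freedom.** The model fits the three arms jointly with one stated covariance structure. On the usual reading that this structure is common to the arms, degrees of freedom are pooled over about 25 + 25 + 12 = 62 or 19 + 19 + 9 = 47 subjects. One lost value then changes the t quantile by under 0.1%. If all three arms lose one, the change is about 0.1–0.2%. Either way, step 3 is essentially the whole effect.

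The SD cancels in the ratio, so the percentages also apply to sweat chloride at the same n and correlation.

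**The case against.** The case for leaving note 6 alone is mainly about frequency and size, and most of it stands. Note 6 is a pre-specified rule applied alike to all arms. Week 12 dosing takes place at the site after the assessments, and protocol 10.6 has it supervised. Protocol 9.6 lets the morning dose wait up to 6 hours on clinic days. No document indicates that any subject is affected. The COVID-19 addendum allows in-home visits for this study, which could make the case less rare, but it gives no count.

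A reader might infer more than the documents support in four places:

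- **Washout.** It may look inconsistent that the same subject's off-drug Washout value is mapped while Week 12 is not. It is not inconsistent. Protocol 9.3.1 makes Washout off-treatment by design, the value goes to its own Washout row, and the MMRM uses only Day 15 and Weeks 4, 8 and 12.
- **Imputed last dose date.** A missing last dose date is imputed from, "in descending order priority, the Early Treatment Termination (ETT) visit date, last visit date before the Safety Follow-up" or the drug administration record, which could keep the Week 12 value. This applies only to missing or partial dates, and the SAP adds that the source is chosen as appropriate. It is no evidence against note 6.
- **Late arrival.** A dose more than 6 hours late is to be skipped (protocol 9.6), which may look like a ready route to the problem. It is a strained one. Lateness is known before the measurement, departs from the same-time-of-day requirement, and puts the value more than 18 hours after the evening tablet on the example clock.
- **Larger widening.** The single-arm t with no use of earlier visits gives 2.89 to 2.96 (25 to 24 completers) and 4.45 to 4.70 (12 to 11), or +2.3% and +5.7%. That is not the planned model, which uses earlier visits and pools the arms.

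None of this restores the Week 12 value under the written rule.

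**Conclusion.** The gap is real but minor. As written, note 6 drops a predose Week 12 spirometry or sweat chloride value when the subject last dosed the evening before and does not take that morning's dose. Notes 2a and 5 do not rescue the value.

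The cost per lost value is about 0.7–2.1% in CI width in a VX-561 arm and 1.6–4.6% in the IVA arm. These figures assume one lost value in the arm, Week 8 observed, a Week 8–Week 12 correlation of 0.5–0.8, the completer counts behind the stated precision, and degrees of freedom pooled across arms. The number of such subjects is not in the documents and is probably small.

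A reader might infer that the primary estimate is biased. The documents do not support that: nothing in them links omission of the final dose to arm or outcome.

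**What to change.** Before data lock, add one exception to note 6: spirometry and sweat chloride collected at the Week 12 visit map to Week 12 when the last dose date is the visit date or the day before. Leave note 6 unchanged for all other visits, including ETT, and leave note 5 as it is.

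**Cost.** One line in SAP Appendix A and a small programming change. No new data and no change to study conduct. SAP section 3 already has the plan finalised before data lock and unblinding, so the choice would be made without sight of results.

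**Downside.** If a dose on the day before was also missed, a value further from the last dose could be admitted. On the example clock, with a visit between 08:00 and 14:00:

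- Evening tablet of Day 84 missed: last tablet 08:00 on Day 84, so 24–30 hours.
- The same, if the evening tablet is the active VX-561 dose: last active dose 20:00 on Day 83, so 36–42 hours.
- Morning tablet of Day 84 missed, if the morning tablet is the active one: last active dose 08:00 on Day 83, so 48–54 hours.

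The last two arise because VX-561 is a once-daily regimen given in a twice-daily blinded schedule, so one of the two administrations may be placebo. The public text does not say which. Note 6 as written can already admit such values when the Week 12 dose is then taken, because it compares dates only. Protocol 9.6 has dose times recorded around PK samples, and Week 12 is a PK visit, so these values can be listed.

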3 SCHEDULE OF ASSESSMENTS

The schedule of assessments is provided in [Table 3-1](#).

Table 3-1 Study VX18-561-101: Screening Visit, Treatment Period, Washout Visit, and Safety Follow-up Visit

Event/Assessment ^a	Screening Visit ^b	Treatment Period					Washout Visit	ETT Visit ^c	Safety Follow-up 28 (± 7) Days After Last Dose of Study Drug
	Day -28 to Day -1	Day 1	Day 15 (± 3 day)	Week 4 (± 5 days)	Week 8 (± 5 days)	Week 12 (± 5 days)	4 (± 1) Days After Week 12 Visit		
Outpatient visits	X	X	X	X	X	X	X	X	X
Randomization ^d		X							
Demographics	X								
Medical history	X								
Weight ^e	X	X	X	X	X	X		X	X
Height ^e	X								
Vital signs ^f	X	X	X	X	X	X	X	X	X
Pulse oximetry ^f	X	X	X	X	X	X	X	X	X
Physical examination ^g	Complete	Abbrev.		Abbrev.	Abbrev.	Abbrev.		Abbrev.	Abbrev.
Standard 12-lead ECG ^h	X	X		X				X	X
Sweat chloride ^{i,j}	X	X	X	X	X	X	X	X	X

^a All assessments will be performed before dosing, unless noted otherwise. Assessments may be performed in any order when more than 1 assessment is required at a particular time point. Assessments that are collected before and after dosing will only be collected once if study drug is not administered on the day of the visit (i.e., premature discontinuation of study drug treatment).

^b All screening results must be reviewed before randomization, unless noted otherwise.

^c If the subject prematurely discontinues study drug, an ETT Visit should be scheduled as soon as possible after the decision to terminate study drug treatment. Additional PK samples and safety assessments may also be performed at the discretion of the investigator. See Section 9.1.5 for additional details.

^d Randomization may occur on the previous day (Day -1) after eligibility has been confirmed.

^e Weight and height will be measured with shoes off.

^f Vital signs and pulse oximetry will be collected after the subject has been at rest for at least 5 minutes.

^g Complete and abbreviated PEs are described in Section 11.5.3.

^h Standard 12-lead ECGs will be performed in the supine position after the subject has been at rest for at least 5 minutes. See Section 8.2 for information about the ECG assessment for study eligibility.

ⁱ Sweat chloride assessments should be performed at approximately the same time at every visit. See Section 8.1 for information about the sweat chloride assessment for study eligibility.

^j The pre-dose assessment on Day 1 may be performed on the previous day (Day -1) if randomization has occurred.

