9.1.5 Early Termination of Treatment OR Early Discontinuation

If a subject prematurely discontinues study treatment, an Early Termination of Treatment (ETT) Visit should be scheduled as soon as possible after the subject decides to terminate study treatment. Subjects who prematurely discontinue treatment will also be required to complete the Safety Follow-up Visit, approximately 28 (± 7) days after their last dose of study drug. The assessments performed at the Safety Follow-up Visit are listed in [Table 3-1](#).

Subjects who discontinue from study drug dosing for any reason (except withdrawal of consent) will have a final PK blood sample drawn as soon as possible after the decision to discontinue study drug is made. Additional safety assessments may also be performed at the discretion of the investigator, including possible consultation with a specialist consultant. The Vertex medical monitor will be informed about these additional assessments, and any additional data collected (e.g., as the result of an outside consultation) will be considered part of the study record to provide the most complete safety profile of the study drug.

If the ETT Visit occurs 3 weeks or later following the last dose of study drug, then the ETT Visit will replace the Safety Follow-up Visit, and a separate Safety Follow-up Visit will not be required.

If a subject withdraws consent for the study, no further assessments will be performed, and no additional data should be collected. Vertex may retain and continue to use any data and samples collected before such withdrawal of consent.

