9.3 Rationale for Study Elements

9.3.1 Study Design

Subjects will continue their stable IVA treatment through screening, and then be randomized to study drug treatment groups on Day 1 (VX-561 or IVA). The efficacy and PD of VX-561 will be assessed after 12 weeks of randomized treatment. IVA (150 mg every 12 hours [q12h]) is included as a reference arm, but with unequal randomization to provide greater information on VX-561 dose-ranging. After the Treatment Period, a 3- to 5-day Washout Period where subjects will take no CFTR modulators is included to collect additional PK and PD data and enable a more thorough evaluation of VX-561 exposure-response relationships.

Following completion of the Washout Period, subjects will resume their prior therapy with commercial IVA.

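### SAP Appendix A imputes a missing last dose date from visits that can fall after dosing has stopped, and ranks the dosing record last

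*SAP*

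**What the plan says.** SAP Appendix A, Derived Variables 2, covers a last dose date that is missing or only partly reported. The first two sources are ranked "in descending order priority, the Early Treatment Termination (ETT) visit date, last visit date before the Safety Follow-up". The third source comes after these and is worded "or the last study drug administration date from EX SDTM domain, as appropriate". One limit is stated: "The imputation algorithm will ensure the imputed last dose date does not exceed the study participation end date". Nothing is said about keeping a reported month or year.

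The protocol fixes when dosing ends and which visits follow:

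- Table 3-1, footnote p: "The last dose of study drug will be the morning dose on the Week 12 Visit".
- Table 3-1 places the Washout Visit "4 (± 1) Days After Week 12 Visit", and section 9.3.1 describes "a 3- to 5-day Washout Period where subjects will take no CFTR modulators".
- Section 9.1.5 has the ETT Visit scheduled as soon as possible once the subject decides to stop. It sets no upper limit in days and foresees a long gap: "If the ETT Visit occurs 3 weeks or later following the last dose of study drug", the ETT Visit takes the place of Safety Follow-up.

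The last dose date feeds the exposure formula (SAP 8.2.5), the denominators of compliance and percentage of tablets taken (8.2.6) and the end of the treatment-emergent period (8.1). It also feeds note 6 to Table 11-1, under which, apart from Safety Follow-up and Washout, "spirometry and sweat chloride assessments after last dose date will not be mapped to analysis visits".

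**The concern.** Both preferred sources are visits that the protocol places at or after the end of dosing. For a completer who attends Washout, the last visit before Safety Follow-up is the Washout Visit, a day on which the protocol says no CFTR modulator is taken. For an early stopper, the ETT date is an upper bound on the last dose, not an estimate of it. The one source that records dosing directly ranks third. The cap at the end of study participation corrects neither case, because both visits fall on or before that date. The treatment of partial dates also departs from SAP Appendices B and D, which keep the known parts of partial medication and AE dates.

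Two things are at stake. Exposure, compliance and treatment-emergent summaries can be shifted for the affected subjects. Note 6, which is meant to keep off-drug spirometry and sweat chloride out of the analysis visits, can also fail for an ETT visit, because a last dose date set equal to the ETT date means that visit is no longer after it.

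**Working it through.** The plan gives no figure for this rule, so there is none to reproduce. The check is day arithmetic on the documents' own schedule.

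**Inputs.** Week 12 target Day 85 (SAP Table 11-1), ±5 days, so Day 80 to 90; Washout 3 to 5 days later; Safety Follow-up 28 (±7) days after last dose, so 21 to 35 days (Protocol Table 3-1). Exposure = last dose date − first dose date + 1. Percentage of tablets taken = 100 × (dispensed − returned) / (planned per day × exposure). The treatment-emergent period ends at the earlier of last dose + 28 days and study completion. I assume full adherence up to the true last dose, count the last day as a full day, and take Safety Follow-up as study completion.

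**Completer, Week 12 on Day 85.**
- Imputed last dose: 85 + 3 = Day 88 to 85 + 5 = Day 90. Exposure is 88 to 90 days instead of 85.
- Tablets taken: 100 × 85/88 = 96.6% to 100 × 85/90 = 94.4%, instead of 100%.
- Treatment-emergent period, for a shift of w days and Safety Follow-up s days after the true last dose: extension = min(w + 28, s) − min(28, s). With s = 21 or 28 this is 0. With s = 35 it is w, that is 3 to 5 days.
- Exposure category: with Week 12 on Day 80 and Washout 5 days later, exposure goes from 80 to 85 days. Twelve weeks is 84 days, so the subject moves from the >8 to ≤12 weeks category to >12 weeks.
- Week 12 efficacy values: the Week 12 window for spirometry and sweat chloride closes at the Week 12 visit date, and Washout uses the nominal visit. Neither value changes.

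**Early stopper, assumed true last dose on Day 40, ETT gap g days.** Exposure becomes 40 + g, and tablets taken 100 × 40/(40 + g):
- g = 0: 40 days, 100%
- g = 7: 47 days, 85.1%
- g = 14: 54 days, 74.1%, below the 80% cut used for compliance in SAP 8.2.6
- g = 21: 61 days, 65.6%

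For g under 21 the treatment-emergent extension is min(g + 28, s) − min(28, s), at most 7 days (s = 35). For g of 21 or more, ETT replaces Safety Follow-up and study completion falls at day g. The extension is then g − min(28, g): 0 up to g = 28, and 7 at g = 35.

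**Mapping of ETT efficacy data.** With g = 14 the ETT falls on Day 54, inside the Week 8 window (43, 71]. On the true last dose date (Day 40), note 6 excludes it. With the last dose imputed as Day 54, the visit is not after the last dose date and its off-drug values could be used for Week 8 if nothing lies closer to Day 57. Day 15, Week 4 and Week 8 are all in the MMRM (SAP 8.3.1.2), and sweat chloride is analyzed similarly (8.3.2.2). Note 5 maps nothing to Week 12 when there is no Week 12 visit, so the ETT value cannot become a Week 12 value. It reaches the Week 12 adjusted mean only through the model's covariance with earlier visits.

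**The case against.** The strongest objection is that this is a contingency rule for rare cases. The Week 12 morning dose is given at the site (Protocol 9.6) under supervision (10.6), and its date and time are recorded because a PK sample is taken that day. A Week 12 attender should seldom lack a last dose date. The documents also do not say what EX holds. If the missing date is itself the final EX end date, the last complete EX date may belong to an earlier interval and be too early. Putting EX first without conditions could then discard genuine on-treatment data. The words "or the last study drug administration date from EX SDTM domain, as appropriate" also leave some discretion.

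Most of this stands as a limit on frequency and on the form of the fix. It does not defend the order: the text sets a descending priority, and no reason is given for preferring a Washout date to the Week 12 date.

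A reader might also infer larger harms that the documents do not support:

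- That ETT values taken 21 days or more after the last dose enter the primary model. Such a visit replaces Safety Follow-up, and note 4 maps it there.
- That Week 12 values are contaminated. Note 5 and the Week 12 window prevent it.
- That the treatment-emergent period is always 3 to 5 days too long for completers. Study completion also caps it, so the shift can be 0.
- That the imputed date is always late. An ETT on the last dosing day gives no error, and a subject with neither ETT nor Washout could be given an on-treatment visit date that is too early.

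**Conclusion.** The point holds as a defect in a contingency rule. For a completer who attends Washout and is dosed as scheduled, the rule as written gives a last dose date 3 to 5 days late, with modest effects on exposure and tablets taken and 0 to 5 days on the treatment-emergent period. For an early stopper whose ETT follows the last dose, exposure is overstated by the whole gap. With a gap under 3 weeks, off-drug ppFEV1 and sweat chloride could enter the models at a visit before Week 12. This last step assumes that ETT efficacy values follow the ordinary visit windows once note 6 no longer excludes them; note 4 states the windowing of other ETT visits only for safety analysis.

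The documents do not say how many last dose dates are missing or partial; the number is probably small. Early stopping itself is not hypothetical: SAP 8.3.1.2 says that most of the 17 subjects in the two discontinued arms did not complete treatment. Those arms are outside the MMRM but remain in the exposure, safety and descriptive ppFEV1 summaries. Nothing here supports a claim that the primary result is materially biased.

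**What to change.** Rewrite Derived Variables 2 in SAP Appendix A before database lock, in this order:

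1. The last administration date in EX, when it is complete and covers the final dosing interval.
2. Otherwise, for subjects who attended Week 12, the Week 12 visit date.
3. Otherwise the ETT date or, if there is no ETT, the date of the last on-treatment visit, limited by any reported month and year.

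State that the Washout Visit date is never used. Add to note 6 that when the last dose date was imputed from the ETT date, that visit's spirometry and sweat chloride are not mapped to on-treatment analysis visits. ETT must stay as a fallback; otherwise an early stopper with no other date would have no exposure or treatment-emergent period. It would also help to report how many last dose dates were imputed and from which source.

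The cost is a few sentences, slightly more derivation work, and the loss of a few ETT values that may in fact have been on treatment.
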